### 10.2.3 Adverse events of special interest and safety topics of interest

AESI (in the opinion of the investigator) will be flagged in the study database. In addition, an AESI is considered to have occurred if any TEAE which meets the Hy's Law criteria, defined as  $\geq 3x$  upper limit of normal (ULN) alanine aminotransferase (ALT) or aspartate aminotransferase (AST) with coexisting  $\geq 2x$ ULN total bilirubin in the absence of  $\geq 2x$ ULN alkaline phosphatase (ALP), with no alternative explanation for the biochemical abnormality. Hy's law criteria will be summarized as described in Section 10.3.

TEAEs are defined as Safety Topics of Interest and reported as follows:

1. Infections (serious, opportunistic, fungal and TB)

- Serious infections will be identified based on MedDRA classification (SOC “Infections and infestations”). (Although not required by the ‘Safety Topics of Interest for the Bimekizumab Program’ document, a separate table will be created for these events.)
- Fungal infections will be summarized in a stand-alone table. The table will include all TEAEs (serious and non-serious) which code into the High Level Group Term “Fungal infectious disorders”.
- Opportunistic infections (including TB) will be summarized in a stand-alone table. The table will include all opportunistic infection TEAEs identified using UCB-defined search criteria which were adjudicated as opportunistic infections. The process for identifying opportunistic infections is outlined in [Section 12.4](#).

## 2. Malignancies

- One table will be based on the criteria standardized MedDRA query (SMQ) = “Malignant or unspecified tumours (SMQ)”.
- One table will be based on the criteria SMQ = “Malignant tumours (SMQ)”.

SMQ search should include all TEAEs which code to a PT included in the Scope = Narrow group within each SMQ.

Note that the events included in the “Malignancies” table will be a subset of the events included in the “Malignancies (including unspecified)” table. While the “Malignant tumours (SMQ)” is most relevant, “Malignant or unspecified tumours (SMQ)” must be reviewed for potential malignancies.

The output tables will include 2 different overall incidence rows:

- The first overall incidence row will summarize “Any Malignancy” and this row will summarize the incidence of all AEs flagged for inclusion in the table (using the appropriate SMQ depending on the table), regardless of the HLT it codes to.
- The second overall incidence row will summarize “Any Malignancy excluding non melanomic skin cancers HLT” and this row will summarize the incidence of AEs flagged for inclusion in the table (using the appropriate SMQ depending on the table), excluding those which code to an HLT of “skin neoplasms malignant and unspecified (excl melanoma)”.

## 3. MACE

Major adverse cardiac events will be presented in a table. The classification of an event as MACE is determined by an external cardiovascular event adjudication committee.

A separate table and listing will present adjudicated cardiovascular events by type. For each cardiovascular event type (24 in total), the individual PTs which fall within each event type will be summarized.

Extended MACE events will be presented in a separate table and listing. All events which are classified by the adjudication committee as any of the event types in [Table 10-3](#) will be considered an extended MACE event.

**Table 10-3: Extended MACE types**

Event Type Code	Event Type
1	Non-Fatal Myocardial Infarction (MI)
2	Non-Fatal Stroke: hemorrhagic
3	Non-Fatal Stroke: ischemic
4	Non-Fatal Stroke: embolic
5	Non-Fatal Stroke: undeterminable
6	Hospitalization or ER for Unstable Angina with urgent revascularization
8	Hospitalization for Heart Failure
10	Coronary Revascularization Procedures (e.g. percutaneous coronary intervention, coronary artery bypass grafting)
11	Urgent Revascularization Procedures (i.e. due to symptoms of brain ischemia or pending infarction)
18	Death due to Myocardial Infarction (MI)
19	Death due to Stroke
20	Sudden Cardiac Death
21	Other CV Death (e.g. heart failure, pulmonary embolism, cardiovascular procedure-related)
22	Cardiovascular Undetermined Cause of Death (ie, cause of death unknown)

CV=cardiovascular; ER=emergency room; MI=myocardial infarction.

Additionally, a listing of all events identified for potential review by the cardiovascular event adjudication committee will be produced. This listing will indicate whether each event was escalated to the committee for formal review/adjudication.

#### 4. Neutropenia

A table will be created based on the following PTs (regardless of seriousness):

- Autoimmune neutropenia
- Band neutrophil count decreased
- Cyclic neutropenia
- Febrile neutropenia
- Idiopathic neutropenia
- Neutropenia

- Neutropenic infection
- Neutropenic sepsis
- Neutrophil count decreased

#### 5. Suicidal Ideation and Behavior

An external neuropsychiatric adjudication committee will evaluate potential neuropsychiatric events and determine whether any of those events were associated with suicidal ideation and behavior (SIB). A table and listing for SIB events as determined by the adjudication committee will be produced.

Additionally, a listing of all events identified for potential review by the neuropsychiatric adjudication committee will be produced. This listing will indicate whether each event was escalated to the committee for formal review/adjudication. A separate listing will also be produced to summarize the adjudicated results of all events escalated to the full committee.

#### 6. Inflammatory bowel disease

An external IBD adjudication committee will evaluate potential IBD events and will classify these according to the event type in [Table 10-4](#).

**Table 10-4: Inflammatory bowel disease types**

Event Type Code	Event Type
1	Possible IBD – Crohn’s Disease
2	Probable IBD – Crohn’s Disease
3	Definite IBD – Crohn’s Disease
4	Possible IBD – Ulcerative Colitis
5	Probable IBD – Ulcerative Colitis
6	Definite IBD - Ulcerative Colitis
7	Possible IBD - Unclassified
8	Probable IBD - Unclassified
9	Definite IBD - Unclassified
10	Symptoms not consistent with IBD
11	Possible IBD – Microscopic Colitis
12	Probable IBD – Microscopic Colitis
13	Definite IBD - Microscopic Colitis
14	Possible IBD – no further differentiation possible
15	Probable IBD – no further differentiation possible

**Table 10-4: Inflammatory bowel disease types**

Event Type Code	Event Type
16	Definite IBD - no further differentiation possible
99	Not enough information to adjudicate

IBD=inflammatory bowel disease.

A table for adjudicated definite IBD events (including event type codes 3, 6, 9, 13 and 16), as determined by the adjudication committee, will be presented for all subjects and stratified by previous medical history of IBD. Previous medical history of IBD will be determined using the information recorded on the Extra-Articular Assessment form at Screening in PA0008 ("Does subject have a history of IBD?").

Similar tables will be presented for adjudicated probable IBD events (including event type codes 2, 5, 8, 12 and 15) and adjudicated possible IBD events (including event type codes 1, 4, 7, 11 and 14). These tables will be produced for all subjects and stratified by previous medical history of IBD as defined above.

A listing of all events identified for potential review by the IBD adjudication committee will be presented. This listing will indicate whether each event was escalated to the committee for formal review and adjudication.

A separate table and listing will present the adjudicated IBD events by type. For each of the 17 IBD event types (event type codes 1 through 16 and 99), the individual PTs which fall within each event type will be summarized.

Finally, a separate listing will be presented showing individual diagnostic criteria met for each adjudicated IBD event.

#### 7. Hypersensitivity (including Anaphylaxis)

A separate table will be prepared based on the MedDRA anaphylaxis algorithm ([Section 12.5](#)) for acute anaphylactic events (reported on the same day as when an injection was administered or one day after). An AE glossary table will also be produced to summarize the MedDRA coding for these events. The glossary table will include the following fields: reported term, PT, LLT, HLT, and SOC.

A separate table will be prepared to summarize hypersensitivity events, identified using the SMQ "Hypersensitivity (SMQ)". All TEAEs which code to a PT included in the Scope=Narrow search will be included in this table. An AE glossary table will also be produced to summarize the MedDRA coding for these events. The glossary table will include the following fields: reported term, PT, LLT, HLT, and SOC.

Injection site reactions will be evaluated based on the "any TEAE" table by looking under the following HLTs: "Administration site reactions NEC" and "Injection site reactions".

#### 8. Hepatic events and DILI

A table for hepatic events will be created based on the SMQ of “Drug related hepatic disorders - comprehensive search (SMQ)”. However, these 2 sub-SMQs are to be excluded: “Liver neoplasms, benign (incl cysts and polyps) (SMQ)” and “Liver neoplasms, malignant and unspecified (SMQ)”. For each of the above SMQs, all TEAEs will be included which code to a PT included in the Scope=Broad and/or Scope=Narrow.

Note that all AEs meeting the above criteria will be included and will not be limited to events that the Investigator determined to be related to study drug.

The incidence of AEs defined as Safety Topics of Interest will be summarized by MedDRA SOC, HLT, and PT (apart from the summary of each cardiovascular event type which will use PT only). The EAIR with associated 95% CI and the EAER will be included in the summary tables.

#### 10.2.4 Impact of COVID-19

In order to assess the impact of the COVID-19 global pandemic on the primary safety endpoint of incidence of TEAEs and serious TEAEs, additional listings and summaries will be presented.

For reporting purposes AEs will be assigned to ‘Prior to COVID-19 pandemic’ or ‘During the COVID-19 pandemic’ based on the following:

- If the date of AE onset (based on imputed start date) is prior to 11 March 2020 the AE will be assigned as ‘Prior to COVID-19 pandemic’
- If the date of AE onset (based on imputed start date) on or after 11 March 2020 the AE will be assigned as ‘During the COVID-19 pandemic’
  - The date of 11 March 2020 is chosen as the date the World Health Organization declared COVID-19 as a pandemic.

A ‘Post the COVID-19 pandemic’ phase will not be assigned for AE reporting as the pandemic is expected to be ongoing at the time of last subject last visit.

The following categories of TEAE will be summarized by MedDRA SOC, HLT and PT, including EAIR and EAER:

- All TEAEs by time of onset relative to COVID-19 pandemic (‘Prior to COVID-19 pandemic’ and ‘During the COVID-19 pandemic’)
- All TEAEs by time of onset relative to COVID-19 pandemic (‘Prior to COVID-19 pandemic’ and ‘During the COVID-19 pandemic’) and by region
- All serious TEAEs by time of onset relative to COVID-19 pandemic (‘Prior to COVID-19 pandemic’ and ‘During the COVID-19 pandemic’)
- All serious TEAEs by time of onset relative to COVID-19 pandemic (‘Prior to COVID-19 pandemic’ and ‘During the COVID-19 pandemic’) and by region
- All COVID-19 related TEAEs by treatment at completion of PA0008 and overall
  - COVID-19 related TEAEs will be identified based on the verbatim term including the text string ‘COVID’. These will include confirmed or suspected COVID-19 infections.

- All COVID-19 related TEAEs by treatment at completion of PA0008 and overall, and by region

The following categories of TEAE will be summarized by MedDRA SOC, HLT and PT:

- TEAEs leading to study discontinuation and/or permanent withdrawal of study medication by time of onset relative to COVID-19 pandemic ('Prior to COVID-19 pandemic' and 'During the COVID-19 pandemic')
- TEAEs leading to study discontinuation and/or permanent withdrawal of study medication by time of onset relative to COVID-19 pandemic ('Prior to COVID-19 pandemic' and 'During the COVID-19 pandemic') and by region

A separate listing of all COVID-19 related AEs will be presented, where COVID-related AEs are identified as described above. In addition, the time of onset of each AE relative to the COVID-19 pandemic will be flagged in all AE listings.

For the purpose of calculating EAIR and EAER prior to and during the COVID-19 pandemic the rules in [Table 10-5](#) will be applied in the calculation of exposure time at risk. An individual subject may therefore be counted in the denominator for both periods ('Prior to COVID-19 pandemic' and 'During the COVID-19 pandemic') dependent on whether the subject is still considered at risk on 11 March 2020. In this case time at risk will be calculated separately for each period. Subjects who have discontinued study medication prior to 11 March 2020 may be included in the denominator for the 'During the COVID-19 pandemic' period if they are still considered to be at risk following the last dose of study medication in the 'Prior to COVID-19 pandemic' period.

Subjects who are no longer in the exposure time at risk period ([Table 10-2](#)) on 11 March 2020, will not be counted in the denominator for the 'During the COVID-19 pandemic' period.

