**Figure 2–1: Schematic Diagram**

Q4W=every 4 weeks; sc=subcutaneous; SFU=Safety Follow-up

Note: Self-administration will be allowed after 3 months of treatment (from PA0009 Week 16 onwards) as described in [Table 2-1](#).

a Subjects will receive their final dose of study drug on PA0009 Week 100 and the SFU Visit will be conducted 20 weeks after the last dose of investigation medicinal product (IMP).

A schedule of study assessments is provided in [Table 2-1](#).

This document cannot be used to support any marketing authorization application and any extensions or variations thereof.

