## 8.5 Impact of COVID-19

Additional sensitivity analyses as a result of the global COVID-19 pandemic are not anticipated as the onset of the pandemic was subsequent to all subjects completing Week 48; therefore, there is no impact on the analysis of the secondary efficacy endpoint.

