**Table 10-2: Exposure time at risk**

Exposure Category	Start Date	End Date	Duration of Exposure
Subjects who died d	Start date for each option as above	Date of death	End date – start date + 1

BKZ=bimekizumab; LD=loading dose.

a 140 days refer to 5 half-lives of BKZ.

b Date of last clinical contact for each subject is defined as the maximum of [last visit date including SFU visit, last AE start date (including imputed AE start dates), date of study termination or completion, last date of study drug administration following rules for partial treatment end dates as per [Section 4.2.5](#)].

c In the event that the first dose in PA0009 was more than 140 days after the last dose in PA0008, the exposure time at risk for 320mg will be calculated using PA0008 end date – PA0008 start date + 140 days.

d For subjects who died, the date of death will be used to replace the end date in the calculation of exposure time at risk only if the subject died within the ‘at risk’ interval (ie, within 140 days following the last dose [not applicable for duration on BKZ 320mg]) or if the subject died before dosing in PA0009 (for time at risk on BKZ 320mg). If the subject died more than 140 days after the last dose of BKZ in PA0009 the exposure time at risk will be calculated using the ‘at risk’ interval of 140 days. Note that date of death should be equivalent to date of last clinical contact.

In the event that a subject received an incorrect (unplanned) treatment sequence the calculations for study medication duration and exposure time at risk will be adjusted accordingly following the principles outlined above and this will be documented in the relevant dataset specifications.

Three summaries of exposure will be provided: 2 for exposure in PA0009 and 1 for exposure in PA0008 and PA0009 combined:

- For the PA0009 summary, durations of exposure and times at risk will be summarized by treatment group at completion of PA0008 and overall. This summary will be repeated by SS Sub-population.
- For the PA0008 and PA0009 combined table, the duration of exposure and time at risk for ‘BKZ 160mg/BKZ 160mgLD combined’, ‘BKZ 320mg’ and ‘BKZ Total’ will be summarized. Subjects who took bimekizumab 320mg during PA0008 will contribute to all three columns. Subjects who did not take 320mg in PA0008 will contribute to the ‘BKZ 160mg/BKZ 160mgLD’ and ‘BKZ Total’ columns.

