### 10.2.2 Exposure-adjusted incidence rate and exposure-adjusted event rate

The time at risk (in days) at AE onset is the same as the time since first bimekizumab dose as described in [Section 10.2.1](#).

Total time at risk (as defined in [Section 10.1](#)) and time at risk at AE onset will be divided by 365.25 to give years at risk.

EAIR and EAER will be calculated separately for tables including all events in PA0008 and PA0009 combined, and for tables including events with onset in PA0009 only. The former tables will use time at risk relative to the start date of bimekizumab 160mg/160mgLD or 320mg (for the 'BKZ 160mg' [this includes both BKZ 160mg and BKZ 160mgLD] and 'BKZ 320mg' columns) and time at risk relative to the date of the first dose of bimekizumab (for the 'BKZ Total' column). The latter table will use time at risk relative to the start date of study medication in PA0009.

The EAIR is defined as the number of subjects with a specific AE adjusted for exposure and will be scaled to 100 subject-years:

$$EAIR = 100 * \frac{n_{AE}}{\sum_{i=1}^{n_{AE}} T_{Exp,i} + \sum_{j=1}^{n_{noAE}} T_{Risk,j}} \quad (23)$$

where  $n_{AE}$  is the number of subjects with the AE,  $T_{Exp,i}$  is a subject's time at risk at AE onset in years (equation [16] in years) and  $T_{Risk,j}$  is the total time at risk in years for subjects who did not experience the AE of interest.

If a subject has multiple events at the level of coding evaluated, the time at risk at AE onset is calculated from the first occurrence of the AE.

Exact Poisson 95% CIs for incidence rates are calculated using the relationship between the Poisson and the chi-square distribution (Ulm, 1990; Fay and Feuer, 1997):

$$LCL = \frac{\chi_{2n, \frac{\alpha}{2}}^2}{2} \quad (24)$$

$$UCL = \frac{\chi_{2(n+1), 1-\alpha/2}^2}{2} \quad (25)$$

$$CI_{Lower} = 100 * \frac{LCL}{\sum_{i=1}^{n_{AE}} T_{Exp,i} + \sum_{j=1}^{n_{noAE}} T_{Risk,j}} \quad (26)$$

$$CI_{Upper} = 100 * \frac{UCL}{\sum_{i=1}^{n_{AE}} T_{Exp,i} + \sum_{j=1}^{n_{noAE}} T_{Risk,j}} \quad (27)$$

where  $n_{AE}$  is the number of subjects with the AE and is the basis for the number of the degrees of freedom for the chi-square quantile for the upper tail probability  $\chi^2$ ,  $T_{Exp,i}$  is a subject's time at risk at AE onset in years,  $n_{noAE}$  is the number of subjects without the AE and  $T_{Risk,j}$  the total time at risk for subjects who did not experience the AE.

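### EAIR and EAER for COVID-19-related TEAEs default to the whole PA0009 time at risk, of which about 40% or more precedes the pandemic in a nominal completer

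*SAP*

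**What the plan says.** SAP 10.2.4 opens one list of tables with the words "The following categories of TEAE will be summarized by MedDRA SOC, HLT and PT, including EAIR and EAER". Six tables follow. The first four cover all TEAEs and serious TEAEs, and each is split into a prior-to-pandemic and a during-pandemic column. The last two are "All COVID-19 related TEAEs by treatment at completion of PA0008 and overall" and the same table by region. Neither has a period split.

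The section then sets out special time-at-risk rules, beginning "For the purpose of calculating EAIR and EAER prior to and during the COVID-19 pandemic the rules in" and pointing to Table 10-5. There the during period starts on 11 March 2020, and subjects no longer at risk on that date are left out of its denominator. On the cut-off the SAP says: "The date of 11 March 2020 is chosen as the date the World Health Organization declared COVID-19 as a pandemic".

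For tables restricted to events with onset in PA0009, the general rule in SAP 10.2.2 is: "The latter table will use time at risk relative to the start date of study medication in PA0009". Table 10-2 ends that time at the last dose plus 140 days or at last clinical contact, whichever is shorter.

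SAP 8.5, explaining why no extra efficacy sensitivity analysis is needed, states that "the onset of the pandemic was subsequent to all subjects completing Week 48".

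**The concern.** The two COVID-19-related tables report rates, have no prior and during columns, and are not mentioned in the rule that invokes Table 10-5. By the written rules they fall back on 10.2.2 and Table 10-2, so the clock starts at the first PA0009 dose. By the SAP's own account, that time includes at least 48 weeks before the pandemic for anyone who was still in the study, when there was essentially no COVID-19 risk. It also includes the entire time at risk of subjects whose at-risk period ended before 11 March 2020.

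A reader will take a COVID-19 rate per 100 subject-years on an immunomodulator as the frequency of COVID-19 while subjects faced the pandemic. On the default denominator the rate is diluted, and by an amount that depends on when subjects entered. The other EAIR and EAER tables in the same section already have the period-specific denominator. The tables that count COVID-19 itself do not.

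**Working it through.** **Inputs**
- Last dose in a completer: "Subjects will receive their final dose of study drug on PA0009 Week 100" (SAP Figure 2-1), i.e. 100 × 7 = 700 days after the first dose.
- At-risk tail: "140 days refer to 5 half-lives of BKZ" (SAP Table 10-2, footnote).
- Pre-pandemic minimum: Week 48 (SAP 8.5), i.e. 48 × 7 = 336 days.
- Visit window: ±7 days (SAP Table 2-1, footnote a).

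**Step 1: reproduce the plan's figure.** Completer time at risk (Table 10-2) = 700 + 140 = 840 days = 120 weeks. This matches the maximum study duration of 120 weeks in SAP section 2.

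**Step 2: pre-pandemic share.** 336 / 840 = 40.0% (337 / 840 = 40.1% if both end days are counted).

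**Step 3: effect on EAER (equation 28).** If all events start on or after 11 March 2020, the numerator is the same under both denominators. Then default rate / during rate = (840 − 336) / 840 = 504 / 840 = 0.60. The default rate is 40% too low; the during-period rate is 840 / 504 = 1.67 times as high.

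**Step 4: effect on EAIR (equation 23).** Subjects with an event contribute time from the first PA0009 dose to onset, so they keep all their pre-pandemic time and lose only time after onset. The dilution is slightly larger. Illustration (assumed 200 completers, 337 pre-pandemic days each, cases evenly spread over the remaining 503 days; rates per 100 subject-years):

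| Cases | EAIR default | EAIR during | Ratio | EAER ratio |
|---|---|---|---|---|
| 4 | 0.875 | 1.467 | 0.596 | 0.599 |
| 10 | 2.207 | 3.724 | 0.593 | 0.599 |
| 20 | 4.482 | 7.644 | 0.586 | 0.599 |

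**Step 5: range for a single subject**
- Week 48 visit 7 days early and Week 100 dose 7 days late: 329 / 847 = 38.8%.
- Last contact at Week 104, no Safety Follow-up visit: 336 / (728 + 1) = 336 / 729 = 46.1%.
- Pandemic reached at the subject's Week 60, 72, 84 or 96: 60/120, 72/120, 84/120 or 96/120 = 50%, 60%, 70% or 80%.
- At-risk time over before 11 March 2020: 100%.

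**Step 6: pooled size, under assumptions only.** Week 48 is the bound set by the last subject to enter. Suppose that subject reached Week 48 exactly on 11 March 2020, entry was even over 26, 39 or 52 weeks, and everyone completed. Mean pre-pandemic time is then 48 + 13 = 61, 48 + 19.5 = 67.5 or 48 + 26 = 74 weeks. The during-period rate would be 120/59 = 2.0, 120/52.5 = 2.3 or 120/46 = 2.6 times the default rate. The documents give no enrolment dates, so these figures only show how the dilution grows with the length of the entry period.

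**The case against.** The strongest reply is that EAIR and EAER in this SAP are rates per 100 subject-years of bimekizumab time at risk, and that the default applies that definition uniformly. With the full denominator, the COVID-19 EAER is on the same scale as the main PA0009 TEAE table and shows how much COVID-19 adds to the overall rate. That is a legitimate quantity. But the SAP does not label it so, and the natural reading of a COVID-19 rate in a pandemic-impact section is the rate during the pandemic.

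It can also be said that no sentence names the denominator for these two tables, and that a programmer might apply Table 10-5 on the strength of its title. This stands in part: the full-PA0009 denominator is a default, not an explicit statement. It is nevertheless what the written rules produce, and the same edit is needed if Table 10-5 was intended.

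Third, the all-TEAE tables split by period, overall and by region, use Table 10-5 and run down to preferred term, so during-pandemic rates for individual COVID-19 terms will exist. This softens the point but does not remove it. Those tables give neither the pooled grouping defined by the COVID text string nor a split by PA0008 treatment group.

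A reader might also infer that the comparison between the 160mg and 320mg groups is confounded by enrolment timing. The documents do not support that. PA0008 was randomized, the columns are reached through its planned treatment sequences, and nothing suggests that entry dates differ between them. Between regions, an effect of entry timing is possible but not shown.

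**Conclusion.** The point holds. Under the SAP's default rule, the EAIR and EAER in the two COVID-19-related TEAE tables understate COVID-19 occurrence during the pandemic period by roughly 40% or more in completers. This rests on the nominal schedule, on the statement in SAP 8.5, and on 11 March 2020 as the start of the period.

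Three stronger statements should not be made. First, 40% is not a strict floor for every individual, since permitted visit windows allow about 39%. Second, a COVID-19-related event before 11 March 2020 is not impossible: the date is that of a declaration, suspected infections count, and any earlier event would narrow the gap. Third, multipliers of 2.0 to 2.6 are not established, because they depend on assumed entry dates.

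The reach is limited to the rates in two supplementary descriptive tables. Event counts, subject counts and the primary safety tables do not change. The point is still worth acting on, because these are the rates most likely to be quoted as the COVID-19 experience in this study.

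**What to change.** In SAP 10.2.4, add that EAIR and EAER in the two COVID-19-related TEAE tables (by PA0008 treatment group, and by region):
- use the during-pandemic time at risk of Table 10-5;
- include in the denominator only subjects still at risk on 11MAR2020;
- count time to AE onset from 11MAR2020 as well, since 10.2.2 would otherwise start it at the first PA0009 dose;
- show any COVID-19-related event with earlier onset as a count only, outside the rate.

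The cost is small. The period totals are already derived for Table 10-5; the onset-time variable needs a short extra derivation, because Table 10-5 defines only total time at risk. The drawback is that these rates will no longer share the denominator of the main PA0009 TEAE tables, which a footnote should say.

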### 3.9 Coding dictionaries

Medical history and AEs will be coded using the Medical Dictionary for Regulatory Activities (MedDRA) version 19.0. Medical history conditions will be classified by primary system organ class (SOC) and preferred term (PT). AEs will be classified by primary system organ class (SOC), high level term (HLT) and preferred term (PT).

Prior and concomitant medications will be coded using version SEP2015 of the World Health Organization Drug Dictionary and will be classified by Anatomical Main Group, Pharmacological Subgroup, and PT.

Medical procedures will not be coded.

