### 5.1.1 Impact of COVID-19

A listing of all visits affected by COVID-19 will be presented based on the Enrolled Set including the visit, date of visit, relationship to COVID-19, impact category and a narrative (short description) of the event. This data will be summarized by treatment group at completion of PA0008, and overall for the ES for the following:

- Impact of COVID-19 for any reason
- Impact of COVID-19 for any reason by country

In addition, in order to assess the potential impact of COVID-19 on the collection and reporting of efficacy data a separate listing and summary will be presented to display missing data and data collected via an alternative modality (eg, phone, video call). For the purpose of these displays, missing data will be presented only for visits affected by COVID-19 (as reported on the dedicated eCRF page) ie, missing data at other visits and for other reasons will not be included.

The following efficacy assessments may be collected remotely:

- HADS
- HAQ-DI
- SF-36
- PGADA
- PtAAP
- PsAID-9

For visits conducted remotely (as reported on the dedicated eCRF page), it is not possible to assess MASES, PhGADA, BSA, PASI, LDI, TJC or SJC, and therefore these assessments will be missing at the specified visit. In addition, for any missed visit or a visit conducted remotely, the CRP assessment will also be missing. Such assessments will be considered to be missing as a result of COVID-19. For these visits, it will therefore not be possible to assess DAS28(CRP) and may not be possible to classify the subject as an ACR responder or nonresponder.

A listing will be presented showing each impacted visit based on the FAS. This will include the planned visit, the visit date, and details of the assessments conducted remotely and/or those missing as a result of COVID-19.

These data will be presented in a summary table by treatment group at completion of PA0008 and overall for the FAS.

For both the listing and the summary table, only visits at which efficacy assessments are scheduled will be included.

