## 12.6 COVID-19 data collection

For study visits impacted by COVID-19, additional data will be collected on a separate dedicated eCRF page.

The following information will be reported:

- Specification of the impacted visit (eg, Visit 5)
- Date of the impacted visit
- Category of the impact (multiple categories may apply to the same visit)
  - Visit not done
  - Visit performed out of window
  - Home visit
  - Visit performed by video call
  - Visit performed by telephone
  - Investigational product shipped to study participant
  - Home administration of investigational product by participant or caregiver
  - Home administration of investigational product by a healthcare professional
  - Missed study drug administration/dispensation

- Temporary discontinuation of study drug
- Permanent discontinuation of study drug
- Termination of study participation
- Other
- Relationship to COVID-19
  - Confirmed COVID-19 infection
  - Suspected COVID-19 infection
  - General circumstances around COVID-19 without infection
  - Other

A narrative of the event will also be collected.

This document cannot be used to support any marketing authorization application and any extensions or variations thereof.

REDACTED COPY

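### COVID-19 related TEAEs are found only by the string 'COVID' in the verbatim term, so infections worded otherwise could drop out of the supplementary COVID-19 tables and listing

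*SAP*

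**What the plan says.** SAP 10.2.4 plans two summaries of COVID-19 related TEAEs with EAIR and EAER, both by treatment at completion of PA0008 and overall, the second also by region. The selection rule is one sentence: "COVID-19 related TEAEs will be identified based on the verbatim term including the text string" 'COVID'. The next sentence describes the content: "These will include confirmed or suspected COVID-19 infections". The listing follows the same rule: "A separate listing of all COVID-19 related AEs will be presented, where COVID-related AEs are identified as described above".

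SAP 12.6 describes a second source: "For study visits impacted by COVID-19, additional data will be collected on a separate dedicated eCRF page". Among its four categories of relationship to COVID-19 are "Confirmed COVID-19 infection" and "Suspected COVID-19 infection". The SAP uses this page for study conduct (3.4) and for visit and efficacy-data impact; 5.1.1 says "A listing of all visits affected by COVID-19 will be presented based on the Enrolled Set". Nothing links the page to the TEAE tables.

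On coding, SAP 3.9 says "Medical history and AEs will be coded using the Medical Dictionary for Regulatory Activities (MedDRA) version 19.0". Coded terms play no part in the COVID-19 rule.

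**The concern.** The verbatim term is the investigator's free text. Protocol 9.1.5 asks for a diagnosis in ordinary medical terms and does not require the word 'COVID'. Sites are in six countries (SAP 3.8). 'SARS-CoV-2 infection' satisfies the protocol's instruction and fails the SAP's search. Because the listing is built from the same search, reading that listing cannot reveal what the search missed.

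In the other direction, the string picks up any term that names COVID, such as a vaccine reaction or anxiety about the pandemic. The SAP does not say whether the table is meant to show infections only or anything connected with the pandemic, and it plans no row that would tell them apart.

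At stake is how far the COVID-19 incidence, EAIR and EAER can be interpreted, in a study whose primary objective is long-term safety and which names infections among its safety topics. The same report will also list visits marked as confirmed or suspected infection, and no step is planned to resolve a disagreement between the two sources.

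**Working it through.** The plan gives no figure to reproduce. The check applies the rule literally to nine terms made up for the purpose (not trial data), six describing an infection and three not. The last column is the search proposed in the fix: 'COVID', 'SARS-COV', 'CORONAVIRUS' or 'CORONA VIRUS', ignoring case.

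| Verbatim term (illustrative) | Infection? | 'COVID', exact case | 'COVID', any case | Proposed search |
|---|---|---|---|---|
| COVID-19 infection | yes | found | found | found |
| Suspected COVID-19 | yes | found | found | found |
| Covid-19 pneumonia | yes | missed | found | found |
| SARS-CoV-2 infection | yes | missed | missed | found |
| Coronavirus infection | yes | missed | missed | found |
| Positive SARS-CoV-2 PCR | yes | missed | missed | found |
| Anxiety due to COVID-19 pandemic | no | found | found | found |
| Arm pain after COVID vaccine | no | found | found | found |
| COVID test negative, common cold | no | found | found | found |

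With exact case the rule finds 2 of 6 infections; ignoring case, 3 of 6. The SAP does not say which applies. All 3 non-infection terms are found either way. Ignoring case, the total is 3 + 3 = 6, equal to the number of infections although half of them are wrong, so the two errors can cancel unnoticed. The proposed search finds 6 of 6 infections and still returns the 3 others, which is why review and separate rows are needed.

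**Size.** Let m be the share of infections worded without 'COVID', and f the number of non-infection matches as a share of true infections. Then

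tabulated count / true infections = 1 − m + f.

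Both shares are assumptions, since the documents give neither:

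| m | f = 0 | f = 0.1 | f = 0.3 |
|---|---|---|---|
| 0 | 1.0 | 1.1 | 1.3 |
| 0.1 | 0.9 | 1.0 | 1.2 |
| 0.3 | 0.7 | 0.8 | 1.0 |
| 0.5 | 0.5 | 0.6 | 0.8 |

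The range is 0.5 to 1.3. In the overall column, one missed subject lowers the incidence by 1/200 = 0.5 percentage points at the maximum enrolment of 200, and by more with fewer subjects or within a treatment or region column.

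**Where the error does not reach.**
- The all-TEAE and serious-TEAE tables select on treatment emergence and seriousness, not on the string.
- The prior/during-pandemic split uses onset before or from 11 March 2020 (SAP 10.2.4).
- Serious infections are identified by system organ class (SAP 10.2.3).
- The secondary efficacy endpoints at Week 48 were complete before the pandemic (SAP 8.5).

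**The case against.** The strongest reply is that this is peripheral. A missed event still counts in the main TEAE tables, still appears in the listing of all AEs (SAP 10.2), and is flagged there as starting before or during the pandemic. The visit listing in SAP 5.1.1 already shows relationship to COVID-19 with a narrative, so a reader could compare the two by hand. The eCRF Completion Guidelines cited in protocol 9.1.5 are not available here and might prescribe the term. All of this stands. It limits the importance of the gap but does not close it, because the SAP states no such comparison and cites no wording convention. It does state a 'COVID' prefix for deviations (5.2), and it plans a term list with physician and committee review for opportunistic infections (12.4).

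Four stronger readings are tempting, and the documents do not support them.

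- *That counting non-infection events is an error.* The category is COVID-19 related TEAEs, and the SAP says it will include infections, not that it is limited to them. This is an ambiguity of scope. It misleads only if the table is read as a count of infections.
- *That the by-region table is distorted.* This would need wording habits to differ between North America and Europe, which nothing in the documents shows.
- *That coding could not recover missed events.* SAP 3.9 gives a dictionary version but says nothing about which terms it holds. The point is not needed, because the rule ignores coded terms.
- *That the eCRF page should define the cases.* It is completed per impacted visit, with no stated link to an AE record, so an infection that disturbed no visit would not be on it. It can serve as a cross-check only.

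**Conclusion.** The concern holds as a gap in a supplementary analysis. Followed exactly, SAP 10.2.4 would leave an infection worded without 'COVID' out of the COVID-19 TEAE tables and listing, and those outputs would not distinguish infections from other events that name COVID. Whether any event is actually missed depends on site wording, which the documents do not reveal; the factor of 0.5 to 1.3 rests wholly on the assumed shares. A reader might infer that the primary safety results are at risk. They are not, since the primary variables do not use the string. This is a cheap improvement worth making, not a threat to the study's conclusions.

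**What to change.** Amend SAP 10.2.4 as follows.

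1. Search verbatim terms, ignoring case, for 'COVID', 'SARS-COV', 'CORONAVIRUS' and 'CORONA VIRUS'. Do not shorten to 'CORONA', which also matches 'coronary' in a study that tabulates coronary revascularization (SAP Table 10-3).
2. Reconcile the result, within a stated date window, against visits marked as confirmed or suspected infection on the dedicated eCRF page. Treat a mismatch as a prompt for review, not as automatic inclusion.
3. Have the study physician confirm the final list before database lock.
4. Show confirmed infection, suspected infection and other COVID-related events in separate rows of the tables, and build the listing from the same confirmed list.
5. If the eCRF Completion Guidelines already prescribe the wording, cite them.

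No new data are needed. The cost is SAP wording and one short medical review of a listing.
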